5.8.5.1 Summary for All TEAEs

The number and percentage of subjects who experience TEAEs will be tabulated by SOC and PT using MedDRA dictionary version 23.0. Adverse events will be counted only once for a subject within each PT and SOC. Since a subject may have more than one PT within a SOC, percentages of PT may not sum to the percentages in the SOC (included in DSMB report).

Incidences will be presented by descending frequency of SOC and PT within SOC, and then alphabetically within PT where the incidence is same; this is based on overall subjects then alphabetically in case of a tie.

Missing and partially missing AE start and/or stop dates will be imputed, for the purpose of statistical analysis. All collected data will be presented in listings. Data not subject to analysis according to this plan will not appear in any tables or graphs but will be included only in the data listings.

Adverse events will be coded using the MedDRA version 23.0 or higher.

A treatment related AE is any AE with a relationship to the study device of possibly related or definitely related.

For all TEAEs the following will be summarized:

- Overall summary of any TEAEs presented by SOC/PT
- Overall summary of any TEAEs by worst severity presented by SOC/PT
- Overall summary of any TEAEs by most causal relationship presented by SOC/PT
- Overall summary of any ADE/SADE/UADEs

A Listing of all AEs will be provided. This listing will include a flag identifying if an AE is a TEAE.

5.8.5.2 Summary for serious TEAEs

For all serious TEAEs the following will be summarized (included in DSMB report):

- Overall summary of any serious TEAEs by worst severity presented by SOC/PT
- Overall summary of any serious TEAEs by closest relationship presented by SOC/PT

A listing of all serious AEs will be provided. This listing will include a flag identifying if a serious AE is a TEAE.

A test of hypothesis comparing the proportions of subjects reporting a TEAE throughout the study will be conducted using a Chi-square or Fisher's exact test, as appropriate. The null hypothesis is that there is no difference in proportion between treatment groups, with a two-sided alternative that considers the possibility of a difference in either direction. The number and percentage of subjects reporting a TEAE and the 95% Wilson confidence interval (CI) for the proportion will be presented for each treatment group. In addition, the difference in proportions between the device and control groups and the 95% Wilson CI will be presented. The same statistics and hypothesis testing will be performed for subjects reporting a SAE throughout the study.

All *P* values will be displayed in four decimals and rounded using standard scientific notation (e.g., 0.XXX). If a *P* value less than 0.0001 occurs it will be shown in tables as <0.0001.

5.8.5.3 Adverse Events Leading to Withdrawal

A summary of incidence rates (frequencies and percentages) of TEAEs leading to withdrawal of study device, by treatment group, SOC, and PT will be prepared for Safety Dataset. No inferential statistical tests will be performed.

A data listing of AEs leading to withdrawal of study device provided, displaying details of the event(s) captured on the CRF.

5.8.5.3 Deaths

Deaths, if any, will be provided in a listing only (included in DSMB report).

5.8.6 Laboratory Data

Analyses on hematology, chemistry, coagulation, and other clinical lab tests will consist of the following (included in DSMB):

- Observed values at baseline and each scheduled post-baseline time point, along with change from baseline at each scheduled post-baseline time point

- Number and percentage of subjects with abnormal laboratory tests indicating serious condition at each scheduled time point
- Shift tables, by analyte and by out-of-range flag at each scheduled post-baseline time point compared to baseline per subject, may be produced

Hematology: complete blood count (CBC), neutrophils, total lymphocytes, monocytes, eosinophils, basophils, iron, hemoglobin (Hgb) will be collected at Visit 1, Visit 2 Treatment Period 1, Visit 3 Treatment Period 2, Visit 4 Treatment Period 3, Visit 5 End of Treatment, and Visit 6 EOS.

Chemistry: sodium, calcium (Total), potassium, chloride, bicarbonate, protein (total), albumin, bilirubin (total), aspartate transaminase (AST), alanine aminotransferase (ALT), glucose, and phosphate will be collected at Visit 1, Visit 2 Treatment Period 1, Visit 3 Treatment Period 2, Visit 4 Treatment Period 3, and Visit 6 EOS. Blood urea nitrogen (BUN), creatinine will be collected at Visit 1, Visit 2 Treatment Period 1 Day 1/3/10/17/26, Visit 3 Treatment Period 2 Day 29/31/38/45/54, Visit 4 Treatment Period 3 Day 57/59/66/73/78, Visit 5 End of Treatment, and Visit 6 EOS. Gamma-glutamyl transpeptidase (GGT), alkaline phosphatase (ALP), amylase, lipase, lactate dehydrogenase (LDH), creatinine kinase (CK), hemoglobin A1c (HbA1c), magnesium, cholesterol, triglycerides, high-density lipoprotein (HDL), low-density lipoprotein (LDL), and will be collected at Visit 1 and Visit 6 EOS.

Coagulation: Prothrombin time/ international normalized ratio (PT/INR) will be collected at Visit 1, Visit 2 Treatment Period 1, Visit 3 Treatment Period 2, Visit 4 Treatment Period 3, and Visit 6 EOS. Activated partial thromboplastin time (aPTT) will be collected at Visit 1, Visit 2 Treatment Period 1 Day 1/3/10/17/26, Visit 3 Treatment Period 2 Day 29/31/38/45/54, Visit 4 Treatment Period 3 Day 57/59/66/73/78, and Visit 6 EOS.

Other: Thyroid-stimulating hormone (TSH ultrasensitive) will be collected at Visit 1 and Visit 6 EOS.

The tests will be presented in the standardized units. Any data contains ‘>’ or ‘<’ sign will be converted to numeric for the summary tables. Subject listings will present all data collected (the ‘>’ and ‘<’ signs will be kept) along with toxicity grading. If the standardized value contains the “<” sign, the data used for the summary tables will be derived by extracting the numeric value from the standardized value and subtracting $0.1(N+1)$ to that numeric value, where N is the number of decimals in the numeric value. For example, if the standardized value = “<0.3”, it will be converted to 0.29 for summary statistics in the table. If the original value contains the “>” sign, the data used for the summary tables will be derived by extracting the numeric value from the standardized value and adding $0.1(N+1)$

to that numeric value, where N is the number of decimals in the numeric value. For example, if the standardized value =”>1000”, it will be converted to “1000.1”.

Results for hematology, chemistry, coagulation, and other clinical lab tests will be provided in separate listings. A listing of abnormal laboratory tests indicating serious condition will also be provided. If any laboratory tests are collected at an unscheduled visit post-baseline, the results will be included in the listings.

Labs that can indicate serious condition if outside reference range:

Albumin (g/L) < 1
 AST > 3xULN
 ALT > 3xULN
 Alkaline Phosphatase (U/L) > 400
 Amylase (U/L) > 120
 Bicarbonate (mmol/L) < 18 or > 34
 Total Bilirubin (mg/dL) > 1.2
 BUN (mg/dL) < 7 or > 20
 Calcium (mg/dL) < 8.5 or > 10.5
 Chloride (mmol/L) < 90 or > 110
 Creatine kinase (U/L) > 300
 GGT (U/L) > 125
 Glucose (mg/dL) < 50
 Hematocrit (%) < 30 or > 58
 Hemoglobin (g/dL) < 9
 Lactate Dehydrogenase (U/L) > 250
 Lipase (U/L) > 120
 Magnesium (mg/dL) < 1 or > 2.8
 Neutrophils (%) < 20 or > 90
 Phosphate (mg/dL) < 1 or > 7
 Platelets (x10E3/uL) < 100 or > 800
 Potassium (mmol/L) < 3.2 or > 5.6
 PT INR > 1.3
 PT (sec) > 20
 Sodium (mmol/L) < 130 or > 150
 WBC count (x10E3/uL) < 2.5

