5 STUDY ENROLLMENT AND WITHDRAWAL

5.1 INCLUSION CRITERIA

In order to be eligible for inclusion, all subjects must meet the following criteria:

1. Male and female subjects, ≥ 40 years of age.
2. b2M level > 20 mg/L.
3. On chronic HD due to ESRD for ≥ 12 months.
4. HD performed using standard HF dialyzers (medium cut-off dialyzers are not acceptable).
5. Score on the MoCA ≥ 16 and ≤ 23 .
6. Life expectancy > 6 months (as determined by the investigator).
7. Body mass index (BMI) ≥ 20 and ≤ 36 .
8. If on medications for cognition (e.g., rivastigmine, galantamine, donepezil, memantine), must be on stable regimen for at least 8 weeks prior to Screening and remain on stable dose for the duration of the study.
9. If on antidepressant medications, must be on stable regimen for at least 8 weeks prior to Screening and remain on a stable dose for the duration of the study.
10. Must be on stable regimens (> 4 weeks) of all treatments for concomitant diseases (e.g., diabetes, hypertension, congestive heart failure).
11. The subject must be able to follow the study protocol, receive the treatment in the established timeframe, and continue during the follow-up interval.
12. The subject must have sufficient visual and auditory acuity to reliably complete all study assessments.
13. Provided a signed and dated informed consent form.

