15 SCHEDULE OF EVENTS

15.1 SCHEDULE OF STUDY EVENTS

SECTION 15.1.1 SCREENING AND RUN-IN

Procedures		Visits 1.1 – 1.6: Run-In						
Visit Number	Visit 1: Screening ¹	V1.1	V1.2	V1.3	V1.4	V1.5	V1.6	
Study Week	Week -6 to -2			Week -2 to -1				
Study Day(s)	Days -42 to -14			Days -14 to -1				
Informed consent	X							
Demographics	X							
Medical history	X							
Physical examination	X							
12-lead ECG	X							
Height	X							
Weight	X	X	X	X	X	X	X	
Targeted physical exam		X	X	X	X	X	X	
Vital signs ²	X	X	X	X	X	X	X	
Laboratory tests ³	X		X ⁴				X ⁴	
Serum pregnancy test (WOCBP only)	X						X (V1.5 or V1.6)	
Hemodialysis @ maximum flow rate of 250 mL/min		X	X	X	X	X	X	
MoCA, PHQ-9 ⁵	X							
Cogstate test battery ⁶		Complete a total of two familiarization assessments prior to V2.1						
Blood sample for b2M ⁷	X (local lab)					X		
Blood sample for plasma proteomics ⁷						X		
Adverse events and concomitant medications	X	X	X	X	X	X	X	

1. The Screening Visit may be split to allow for sufficient time to complete all procedures. AEs and concomitant medications should be reviewed during split visits, as applicable.

2. For additional information, see [Section 7.1.1.2.2](#).

3. For additional information, see [Section 7.1.1.1.5](#) and [Section 15.2 Schedule of Laboratory Tests](#).

4. Laboratory testing for BUN, creatinine, and aPTT only. Samples should be taken prior to HD and again mid-way through HD (~2 hrs into treatment). Samples for aPTT may be taken anytime blood clots are suspected in the circuit or at the discretion of the investigator.

5. For additional information, see [Section 7.1.1.1.7](#) and [Section 7.1.1.1.8](#).

6. For additional information, see [Section 7.1.1.3.3](#).

7. For additional information, see [Section 7.1.1.1.9](#). The V1 b2M sample is to be assayed at a local lab for screening purposes. This sample should be collected prior to HD or on a non-dialysis day.

8. For additional information, see [Section 7.2.2.1](#) and [Section 15.2 Schedule of Laboratory Tests](#).

SECTION 15.1.2 TREATMENT PERIOD 1 (VISIT 2/MONTH 1)

Procedures												
Visit	Visit 2: Treatment Period 1											
Visit Number	2.1	2.2	2.3	2.4	2.5	2.6	2.7	2.8	2.9	2.10	2.11	2.12
Study Week	Week 1			Week 2			Week 3			Week 4		
Study Day (± 1 day)	Day 1	Day 3	Day 5	Day 8	Day 10	Day 12	Day 15	Day 17	Day 19	Day 22	Day 24	Day 26
Verify eligibility ¹	X											
Randomization ²	X											
HD (250 mL/min for ~4 h)	X	X	X	X	X	X	X	X	X	X	X	X

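### SAP 5.8.6: the albumin serious-condition limit is effectively unattainable as written, and the BUN upper limit is uninformative for pre-dialysis samples, with the flagged draw left unspecified

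*SAP*

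**What the plan says.** SAP 5.8.6 introduces its list as "Labs that can indicate serious condition if outside reference range". The list flags albumin, given in g/L, when it falls below 1, and it flags "BUN (mg/dL) < 7 or > 20". The laboratory outputs marked for the DSMB in that section include "Number and percentage of subjects with abnormal laboratory tests indicating serious condition at each scheduled time point", and a separate listing of the flagged tests is also planned. The preceding item in the same DSMB output is "Observed values at baseline and each scheduled post-baseline time point, along with change from baseline at each scheduled post-baseline time point".

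Protocol 5.1 requires every subject to be "On chronic HD due to ESRD for ≥ 12 months".

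On sampling, SAP 5.8.6 says "Blood urea nitrogen (BUN), creatinine will be collected at Visit 1, Visit 2 Treatment Period 1 Day 1/3/10/17/26" and continues with matching days in the other two periods, Visit 5 and Visit 6. It does not place these samples relative to the dialysis session. Three other places bear on timing:

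- Protocol 7.1.1.1.5 has Screening samples drawn before dialysis or on a non-dialysis day.
- The Run-in schedule in Protocol 15.1.1 (footnote 4) says of BUN, creatinine and aPTT: "Samples should be taken prior to HD and again mid-way through HD (~2 hrs into treatment".
- SAP 5.8.1 computes the urea reduction ratio (URR), which needs a post-dialysis BUN.

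SAP 5.1 sets Screening as the baseline for clinical laboratory tests.

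**The concern.** A flag count helps a safety board only if the flag separates subjects in trouble from the rest of the study population. An albumin limit of 1 g/L is so low that no realistic fall would reach it. The albumin row would therefore read zero whatever happened, and a reader could take the zero as reassurance. A BUN limit of 20 mg/dL fails in the opposite way for pre-dialysis samples: it would mainly record that the subject has end-stage renal disease.

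The unspecified draw adds a second problem. BUN falls steeply during a session. The flag rate could therefore move from visit to visit, or between Screening and treatment, only because a different draw was used. Safety is the primary objective, and Protocol 8.5 gives no numeric halting rule but leaves continuation to DSMB recommendations. The tables the board reads should therefore be interpretable as they stand.

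**Working it through.** The SAP gives no derivation and no expected flag rate for either limit, so there is no plan figure to reproduce. The documents also give no BUN or albumin distribution. The ranges below are assumptions, and all probabilities are normal tail areas.

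**Albumin**

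1. Unit: 1 g/L = 0.1 g/dL.
2. Assumed mean 25, 30, 35 or 40 g/L with SD 3, 5 or 7 g/L, giving twelve combinations. P(flag) = Φ((1 − mean)/SD).
3. Worst case, mean 25 and SD 7: z = (1 − 25)/7 = −3.43, P = 0.000303. Ten of the twelve combinations give less than 0.000001.
4. SAP 5.8.6 schedules albumin at five visits (1, 2, 3, 4 and 6). With 26 subjects that is up to 26 × 5 = 130 values. Even in the worst case the expected number of flags in the whole trial is 130 × 0.000303 = 0.04.
5. If the unit was meant to be g/dL, the limit is 10 g/L. The worst case is then z = (10 − 25)/7 = −2.14, P = 0.016, and ten of the twelve combinations are below 0.2%.

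**BUN above 20 mg/dL**

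Assumed pre-dialysis mean 40 to 70 mg/dL and SD 12 to 20 mg/dL, with a fall of 40 to 50% by mid-session and 65 to 75% by the end. By the SAP's own URR formula, a later sample exceeds 20 only if the pre-dialysis value exceeds 20/(1 − fall).

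| Draw | Assumed fall | Pre-dialysis value needed (mg/dL) | Flagged |
|---|---|---|---|
| Pre-dialysis | none | 20 | 84 to 100% |
| Mid-session | 40%, 50% | 33.3, 40.0 | about 50 to 100% |
| Post-dialysis | 65%, 70%, 75% | 57.1, 66.7, 80.0 | about 0 to 86% |

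The ends of the ranges:

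- Pre-dialysis low end, mean 40, SD 20: z = (20 − 40)/20 = −1, so 84% lie above.
- Mid-session low end, mean 40, fall 50%: the value needed equals the mean, so 50%.
- Post-dialysis high end, mean 70, SD 12, fall 65%: z = (57.1 − 70)/12 = −1.07, so 86%.
- Post-dialysis low end, mean 40, SD 12, fall 75%: z = (80 − 40)/12 = 3.33, so about 0%.

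With a pre-dialysis mean of 50 or more, the pre-dialysis rate is 93 to 100%.

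**BUN below 7 mg/dL**

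This limb can still fire: about 0 to 5% of pre-dialysis values and up to about 27% of post-dialysis values (mean 40, SD 20, fall 75%: the pre-dialysis value must be below 28, z = (28 − 40)/20 = −0.6). These low-tail figures are rough. In that combination about 2% of the assumed distribution lies below zero (z = −40/20 = −2).

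**Would counting only new flags repair the BUN row?**

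No. If 84 to 100% are already flagged at Screening, at most 26 × 0.16 = 4.2, about four subjects, could ever become newly flagged, and possibly none. The row would change from nearly always to nearly never.

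**The case against.** The strongest reply is that the DSMB does not depend on these flags. The same output gives it observed values and change from baseline for each analyte. SAP 5.1 includes the minimum in continuous summaries, so an extreme albumin value would appear there. Shift tables may also be produced. Under Protocol 8.6 the CRO's medical monitor and/or the sponsor's program physician review laboratory values throughout and can trigger an ad hoc meeting. Under Protocol 7.2.1 clinically significant values are recorded as adverse events. Neither flag feeds the primary endpoint or the escalation rules. All of this stands, and it limits the consequence. It does not make either flag work, and nothing in the documents corrects the albumin limit.

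Four stronger readings are tempting, and the documents do not support them:

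- **That the whole list carries no safety signal.** The other entries are separate. Hemoglobin below 9 g/dL, for instance, matches Protocol Appendix 17.1.
- **That every BUN value would be flagged.** That follows only if one assumes a range lying wholly above 20. Mid-session and post-dialysis draws can fall below it, and the below-7 limb behaves differently.
- **That BUN would swamp the table.** The table shells are in separate files. If results are shown by analyte, a full BUN row hides nothing in the others.
- **That the column strips albumin.** The readable text describes adsorption of b2M only.

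**Conclusion.** The point holds, confined to two entries. The albumin limit is effectively unattainable as written, with a flag probability of at most about 0.0003 per value over the assumed range. It appears to be a unit or limit error, so the albumin row and listing cannot identify a subject with a serious fall. The BUN upper limit is uninformative for pre-dialysis samples, at about 84 to 100% flagged. Its behavior for other draws ranges so widely that the count cannot be interpreted until the draw is named.

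The albumin conclusion is robust to the assumptions. The BUN percentages depend on them and should be read as ranges. Because the DSMB also sees the values themselves and their change from baseline, this is a flaw in two flags and not a gap in laboratory surveillance. It does not affect the primary analysis.

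**What to change.** Amend SAP 5.8.6 as follows:

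1. The sponsor's responsible physician and statistician check and correct the albumin unit or limit.
2. State which BUN draw (pre-, mid- or post-dialysis) the flag uses, and use the same one at every visit.
3. Replace the BUN upper limit with one suited to dialysis patients, or define it relative to the subject's own baseline. The sponsor sets the value; none is proposed here.
4. Show flag prevalence at Screening, the SAP's laboratory baseline, beside the post-baseline counts. Screening samples are never post-dialysis, so the choice in item 2 must allow for that comparison.

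The cost is a short edit to the list, one sentence on sampling time and one extra column in an existing table. No new data are needed for a draw that is already collected, but the database should be checked to confirm that the draw time is recorded.

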5.8.7 Vital Signs

Vital signs, including blood pressure (mmHg), heart rate (beats/min), respiratory rate (breaths/min), and body temperature (C), will be summarized. Seated/reclined BP will be recorded before each dialysis session, every 30 minutes during dialysis, and at the end of the session. Other vital signs will be captured as described in the Schedule of Events, Protocol Section 15.1. Observed values will be tabulated at baseline, and at each scheduled post-baseline time point. Change from baseline at

each scheduled post-baseline time point will also be summarized (included in DSMB report). Change from baseline in blood pressure may also be presented in figures.

Additionally, a ‘Repeated SBP < 90 mmHg or action taken to HD’ listing will be populated if there are two SBP < 90 within 30 minutes of the start of the hemodialysis, or if in the hemodialysis data we have additional saline use entered as ‘Hypotension’, or there is a log record in the hemodialysis data within 30 minutes of a < 90 SBP with a change in blood flow rate, dialysate flow rate, or ultrafiltration rate (this would include if the hemodialysis was stopped). Abnormal vital sign values will be flagged in the listings. Abnormal vital sign values are as follows:

- Seated systolic blood pressure value < 90 mmHg
- Seated systolic blood pressure value > 180 mmHg
- Seated diastolic blood pressure value < 50 mmHg
- Seated diastolic blood pressure value > 110 mmHg
- Incidence of orthostatic hypotension (a decrease in systolic blood pressure of >20 mmHg and/or a decrease in diastolic blood pressure of > 10 mmHg between supine and standing)
- Heart rate > 100 beats per minute
- Temperature > 37.5°C
- Temperature < 36.5°C
- Respiration rate > 20 breaths per minute
- Respiration rate < 12 breaths per minute

5.8.8 Weight

Weight will be collected as described in the Schedule of Events, Protocol Section 15.1. Observed values in lb. will be tabulated at pre-HD and post-HD per HD session. Change from pre-HD at post-HD per HD session will also be summarized (included in DSMB report). A listing of weight (lb.) will be provided.

The initial fluid removal goal, actual fluid removal, amount differs from the goal, the proportion of subjects achieved the fluid removal goal will also be summarized by visit and treatment period. Actual fluid removal = total fluid output - total fluid intake. The amount differs from the goal = actual fluid removal – fluid removal goal.

5.8.9 12-lead ECG

A 12-lead ECG will be performed to obtain Heart rate (beats/min), QT interval (msec), and QT interval corrected by the Fridericia formula (QTcF (msec)). ECGs will be collected at Visit 1 and Visit 6 EOS.

Observed value at baseline and Visit 5, along with the change from baseline value at Visit 5 will be summarized (included in DSMB report).

A Shift table, by ECG test and by overall interpretation from Visit 1 to Visit 6 EOS will be provided.

A listing of all 12-lead ECG will be provided. A listing of abnormal 12-lead ECG will also be provided.

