Title: A Randomized, Double-Blind, Phase 2a Study to Evaluate the Tolerability, Feasibility, and Efficacy of AKST1210 in Patients on Hemodialysis with Cognitive Impairment Associated with End-Stage Renal Disease

Précis: This is a randomized, double-blind study, to be conducted at up to 5 hemodialysis (HD) centers in approximately 20 evaluable subjects randomized in a 1:1 ratio (n=10 per arm) to either the AKST1210 column (the investigational treatment) or to the control (no column), to assess the tolerability, feasibility, and efficacy of AKST1210 (a beta 2-microglobulin [b2M] apheresis column) in subjects with end-stage renal disease with cognitive impairment (ESRD-CI) undergoing HD 3 times per week.

Subjects will undergo a Screening visit followed by a 2-week Run-in period. During the Run-in period, subjects' HD flow rate will be adjusted to a maximum of 250 mL/min. Subjects that meet all inclusion criteria and none of the exclusion criteria will then be randomized to either receive HD with the AKST1210 column or control (i.e., no column). The AKST1210 column will be connected in series before (upstream of) the HD cartridge for the duration of each HD session. The control will consist of a covered surrogate object of similar size/shape as the AKST1210 column which will be set up in such a way to mimic the appearance of an in-line AKST1210 column. The subject, investigator, and outcomes assessor will be blinded as to treatment.

There will be three (3) 4-week treatment periods, and all subjects will receive 3 HD treatments per week for 12 weeks. Subjects who may occasionally require an additional HD session per week would not receive the investigational intervention on that additional day. Subjects randomized to the AKST1210 column will start with a 150 mL column (S-15) used during Weeks 1 to 4 (Treatment Period 1). Subjects who meet specific criteria will undergo escalation of the column size to a 250 mL column (S-25) during Weeks 5 to 8 (Treatment Period 2) and then to a 350 mL column (S-35) during Weeks 9 to 12 (Treatment Period 3). Subjects randomized to control (no column) will receive identical escalation evaluations to maintain the treatment assignment blind. The rules specifying the criteria for escalation, de-escalation, and discontinuation are provided in [Appendix 17.1](#).

Following Treatment Period 3, subjects should resume HD in accordance with standard of care. Subjects will return for an End of Study (EOS) Visit during Week 14.

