3.2 Secondary Endpoints

- Feasibility of all procedures, including blinding.
- Tolerability of each column size escalation, as measured by subject compliance with study visit schedule/completion, visit procedures, and subject retention.
- The change in IDH Rate above each subject's Historical IDH Rate for each column size.
- The incidence of IDH leading to de-escalation or discontinuation.
- The incidence of worsening anemia by column size.
- The incidence of anemia leading to de-escalation or discontinuation.
- Change from baseline in levels of b2M at Weeks 4, 8, 12 and end of study (EOS) and evaluation of any differences in the magnitude of change based on column size and duration of treatment with a specific column size.
- Change in Montreal Cognitive Assessment (MoCA) from baseline to EOS.
- Change in cognitive domains as measured with the Cogstate battery (i.e., verbal learning, psychomotor function, visual attention, working memory, executive function, and verbal delayed recall).
- Change in quality of life per the Short-Form Health Survey (SF-36).
- Change in the Patient Health Questionnaire-9 (PHQ-9).
- Change in sleep quality as measured by the Pittsburgh Sleep Quality Index (PSQI).
- Change in fatigue as measured by the Fatigue Questionnaire – Functional Assessments of Chronic Illness Therapy (FACIT).
- Changes from baseline in laboratory test data, vital sign measurements, and electrocardiograms (ECGs).

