5.7.9 Change from Baseline in MoCA

The MoCA is a 1-page, 30-point test designed as a rapid scoring instrument for mild cognitive dysfunction. The questionnaire assesses several different cognitive domains, including attention and concentration, executive functions, memory, language, visuospatial skills, conceptual thinking, calculations and orientation. Higher scores indicate better cognitive function; the total possible score is 30 and a score of 26 or more is considered normal. Derivation for the MoCA total score = sum of individual item scores, with a range from 0 to 30.

Observed MoCA sub-scores and the MoCA summary score will be summarized by treatment group and Total at baseline, and at Visit 6 EOS. Change from baseline at Visit 6 EOS will also be summarized for sub-scores and summary score. The MoCA summary score are calculated within the EDC; this score will be obtained directly from the EDC data.

Within-group comparison of MoCA summary scores between baseline and Visit 6 EOS will be performed by Wilcoxon signed-rank test and associated P-values will be reported. Additionally, if the change in the MoCA summary score is normal based on Q-Q plot, the mean change from baseline in MoCA total score will be compared between treatment groups using an ANCOVA model with treatment as the main effect and baseline MoCA summary score as the covariate.

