5.7.12 Change in Patient Health Questionnaire-9 (PHQ-9)

Scores will be summated for each subject across the 9 items and the calculated total score will be summarized by treatment group and Total at baseline, and at Visit 6 EOS. Within-group comparison of calculated total scores between baseline and Visit 6 EOS will be performed by Wilcoxon signed-rank test and associated P-values will be reported. Change from baseline at Visit 6 EOS will also be summarized. A listing of PHQ-9, including the total score, will be provided.

Additionally, if the change PHQ-9 total score is normal based on Q-Q plot, the mean change from baseline in PHQ-9 total score will be compared between treatment groups using an ANCOVA model treatment with treatment as the main effect and baseline PHQ-9 total score as the covariate.

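### No 12-lead ECG is scheduled between Screening and about two weeks after the last column session, so a reversible ECG change during device use could be missed

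*SAP*

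**What the plan says.** SAP 5.8.9 gives two collection times for the ECG: "ECGs will be collected at Visit 1 and Visit 6 EOS". The same section then plans the summary table at a different visit: "Observed value at baseline and Visit 5, along with the change from baseline value at Visit 5 will be summarized (included in DSMB report". Its shift table runs from Visit 1 to Visit 6.

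The Protocol schedule matches the collection statement. The ECG appears at Screening (15.1.1) and at Visit 6 (15.1.5). It appears in none of the three treatment-period tables (15.1.2 to 15.1.4) and not at Visit 5.

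PHQ-9 and MoCA follow the same pattern. For PHQ-9, SAP 5.7.12 says "the calculated total score will be summarized by treatment group and Total at baseline, and at Visit 6 EOS". For MoCA, SAP 5.7.9 says "Observed MoCA sub-scores and the MoCA summary score will be summarized by treatment group and Total at baseline, and at Visit 6 EOS", and SAP 3.2 defines the endpoint itself as "Change in Montreal Cognitive Assessment (MoCA) from baseline to EOS".

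The column or control is last used at Visit 5. The Protocol Summary then says: "Following Treatment Period 3, subjects should resume HD in accordance with standard of care".

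**The concern.** Safety and tolerability are the primary objective, and change in ECG is a named secondary endpoint (Protocol 4.2.2, SAP 3.2). Subjects are stepped through up to three column sizes over 12 weeks, yet no scheduled ECG is taken at any size. A change in QTcF or conduction that appears during device use and reverses on stopping could be absent from the ECG tables.

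Protocol 8.6 lists ECGs among the cumulative safety data reviewed throughout the study, and SAP 5.8.9 puts the ECG table in the DSMB report. A subject still on device can contribute only a Screening ECG to either review. If the table is run at Visit 5 as written, it has no scheduled post-baseline data at all.

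PHQ-9 has the same timing, so a reversible mood change could also be missed by that instrument.

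**Working it through.** **Inputs**

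- Last column or control session: Visit 5, Day 82 ± 1 (Protocol 15.1.5).
- EOS: Visit 6, Day 96 ± 3 (Protocol 15.1.5).
- Early withdrawals: encouraged to complete EOS procedures within 4 to 6 weeks of their last visit (Protocol 5.4.2).
- Sessions: three per week for 12 weeks, on the Day 1, 3, 5 pattern of Protocol 15.1.2.

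**The plan's own timing.** Protocol 15.1.5 places Visit 5 in Week 12 and Visit 6 in Week 14. Day 82 falls in Week 12 (Days 78 to 84) and Day 96 in Week 14 (Days 92 to 98), so the figures agree.

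**Gap from last session to the only post-baseline reading (completers)**

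- Nominal: 96 − 82 = 14 days.
- Shortest: (96 − 3) − (82 + 1) = 93 − 83 = 10 days.
- Longest: (96 + 3) − (82 − 1) = 99 − 81 = 18 days.
- Early withdrawals: 4 to 6 weeks = 28 to 42 days, if they use that interval.

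On the weekly pattern, five HD sessions without the column (Days 85, 87, 89, 92, 94) come between Day 82 and Day 96.

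**Scheduled readings during the device period**

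| Measure | Days 29, 57 and 82 | Day 96 |
|---|---|---|
| 12-lead ECG | none | yes |
| PHQ-9 | none | yes |
| MoCA | none | yes |
| Cogstate, SF-36, FACIT, PSQI | all three days | yes |

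**How much of a reversible effect would remain.** The documents give no offset rate, so this is an assumption shown over a range. With exponential decay, the fraction remaining is 0.5^(gap / half-life):

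| Assumed half-life | 10 days | 14 days | 18 days |
|---|---|---|---|
| 2 days | 3.1% | 0.8% | 0.2% |
| 7 days | 37% | 25% | 17% |
| 14 days | 61% | 50% | 41% |
| 28 days | 78% | 71% | 64% |
| no decay | 100% | 100% | 100% |

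The result runs from almost nothing to everything. One reading at Day 96 therefore cannot separate no effect from an effect that has worn off.

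**Dialysis conditions.** The ECG baseline is Screening (SAP 5.1), before Run-in limits the flow rate to 250 mL/min. At Visit 6 the flow rate is per standard of care (Protocol 15.1.5). Neither ECG is taken under study dialysis conditions.

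**What a Visit 5 reading would add.** 3 × 12 = 36 sessions are scheduled. Before HD on Day 82, 36 − 1 = 35 are complete, the latest on Day 80. The gap becomes 82 − 80 = about 2 days. Sample size is unaffected.

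**The case against.** A reader might infer that these endpoints cannot measure any device effect, or that the ECG data could not show harm. The documents do not support that. Results are summarised by arm, and an effect lasting to Day 96 would still appear as a difference between AKST1210 and control. What can be lost is a reversible effect.

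A reader might also infer that mood goes unmeasured on device. SF-36 is given on Days 29, 57 and 82, and SAP 5.7.11 summarises its mental health scale and MCS at each scheduled post-baseline time point. That is partial cover, though not by the same instrument.

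MoCA is not a gap of the same kind. Its time point is declared in the endpoint. Cogstate reads cognition at both Visit 5 and Visit 6, and b2M is sampled at V4.11 and V6 (SAP 5.7.7), so cognition and the target are each seen on and off device.

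For ECG, other monitoring exists: heart rate at the start and end of each visit, blood pressure every 30 minutes during dialysis, AE review at every treatment visit, and DSMB meetings at least quarterly. These can catch symptomatic events but do not measure QTcF. The risk section of the public Protocol is redacted, so whether a cardiac conduction risk was anticipated cannot be judged.

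A Visit 5 ECG has limits too. Taken before HD, it would still miss a change confined to the session. Moving the ECG from Visit 6 would also remove data the shift table needs. In a small, mainly descriptive Phase 2a study, a single post-treatment check is a defensible choice. These points narrow the concern; they do not supply an ECG during the device period.

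**Conclusion.** The point holds in limited form and is strongest for ECG. No 12-lead ECG is scheduled between Screening and Visit 6, which is 14 days after the last session for completers (10 to 18 with windows) and possibly 28 to 42 days for early withdrawals. A reversible ECG or QTcF change during device use could be missed at scheduled visits, and a null result at Visit 6 could not be told from offset. This rests on the schedule alone. The decay table is illustrative and its half-lives are assumed.

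Separately, SAP 5.8.9 and Protocol 15.1.5 conflict on the ECG summary visit and must be reconciled. Relabelling the table to Visit 6 would resolve the conflict but leave the endpoint measured off device.

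PHQ-9 shares the timing, with partial cover from SF-36. MoCA needs only a label. No power or sample-size figure changes. This is an inexpensive improvement to a safety endpoint, not a flaw that invalidates the study.

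**What to change.** 1. In Protocol 15.1.5, add the 12-lead ECG, and preferably PHQ-9, at Visit 5 (Day 82) before HD, alongside Cogstate, FACIT, PSQI and SF-36, which are already given there. Keep the Visit 6 assessments for the shift table and the off-device reading.
2. In SAP 5.8.9 and 5.7.12, report change from baseline to Visit 5 as the end-of-treatment result. State that it is taken about 2 days after the previous session and is not an intradialytic reading.
3. Label Visit 6 values for ECG, PHQ-9 and MoCA as 'about two weeks off device', and note the longer interval possible for early withdrawals.
4. If Visit 5 data can no longer be collected, correct the ECG summary table to Visit 6, apply the same label, and do not conclude that there was no ECG effect during device use. SAP Rev. B is dated 25 August 2021; the documents do not say whether collection was then complete.

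Cost: one resting ECG and a 5 to 7 minute questionnaire per subject, SAP wording, and a protocol amendment that needs IRB approval before implementation (Protocol 12.2). Item 4 alone costs only wording.
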